5.3 Rationale

Vaginismus is the involuntary spasm of the pelvic floor muscles which surround the vaginal wall. It affects roughly 13 to 34% of premenopausal women and 6 to 45% of postmenopausal women (Meana, 2017). Vulvodynia, which has significant overlap with vaginismus, was estimated to affect 16% of women based on a National Institutes of Health (NIH) population-based study (Harlow & Stewart, 2003). Vaginismus can make sexual intercourse uncomfortable, painful, or impossible, and can have resultant impacts on a woman's sexual pleasure and ability to conceive and is associated with depression and anxiety. It can lead to secondary vulvodynia, or vulvodynia can co-exist.

Successful treatment relies often on both medical and psychosocial interventions alongside self-help and practice, although no standardised treatment exists. Current medical therapy for vaginismus often consists of the use of topical local anaesthetic gel, often in addition to oral medications such as low dose Tricyclic Antidepressants together with recommendation of progressive vaginal dilator therapy and physiotherapy. Whilst no one treatment or approach has a high degree of success, a combined approach has been shown to offer the most significant improvements.

Whilst anecdotally, some women find that clitoral stimulation can sometimes have a positive impact on the ability to progress with vaginal dilator treatment and enjoyment of sexual intimacy, this has not yet been evaluated in a research setting. This study looks at the feasibility and acceptability of using clitoral vibration therapy, alongside current therapy, for women with Vaginismus. This has the potential to guide clinicians' recommendations, which are currently not based in evidence, and if found to be acceptable, to pave the way for studies into efficacy.

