This proposed study looks at the feasibility and acceptability of using clitoral vibration therapy, alongside current therapy, for women with vaginismus. It is likely that many, if not most, of these women will also have an element of vulvodynia. We propose that the use of external clitoral or vulval vibration therapy is likely to be acceptable in most women with vaginismus, based on acceptability of vulvar vibration therapy in women with vulvodynia. We propose based on the evidence above that vibrator therapy may help women with female sexual dysfunction to use vaginal dilators, based on study showing improvements with sexual distress and satisfaction.

Enrollment

This is a nonrandomized controlled trial, with the initial cluster of patients receiving standard therapy, and the second cluster receiving standard therapy plus vibrator. We aim to recruit an initial 15 participants who will receive standard therapy, and another 15 who will receive an external vibrator.

We expect this to take place over approximately 24-48 months. Enrollment of patients will be from a joint psychosexual clinic led by a medical doctor and a clinical psychologist. Female patients are referred to this clinic by General Practitioners, from within the Sexual Health service, or via Gynaecologists, frequently with complaint of difficulty or pain with penetrative sex. Inclusion and exclusion criteria have already been outlined.

Trial information will be given at the initial appointment. If the patient wishes to enrol, then an initial baseline questionnaire will be given, and a follow up questionnaire will be filled out by phone contact at 6-24 months afterward the initial consultation at the patients consent.

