6.1 Primary objective

Is vibration therapy (through the use of handheld vibrators on clitoral and vulval area) acceptable to women as part of medical management of vaginismus and vaginismus/vulvodynia, alongside current medical management.

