6.3 Primary endpoint

Baseline and follow up questionnaires will be used – to assess acceptability and perceived acceptability of control therapy and intervention.

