The follow up questionnaires will be filled out by phone contact 6-24 months after the initial consultation at the patients consent if they agree to remain enrolled in the trial for both group 1 and group 2. This will take approximately 30 mins and will be arranged at a time convenient for the patient. This interview will be carried out by a doctor. Answers will be recorded directly onto the follow up questionnaire proforma.

4 point Likert scale 1 (Strongly disagree) to 4 (Strongly agree)

9. Study procedures

- Informed consent – verbal and written will be given, patients will be offered opportunity to enrol on the day (for convenience) or to return at another point to enrol.
- Screening and recruitment – as outlined previously recruitment will be directly from clinic
- Randomization – this is a non-randomized controlled trial, as trial participants need to be identified as time goes on, and a certain number of control and intervention participants are needed. The initial 10-15 recruited will receive standard treatment, and then the next 15 will receive intervention.

Study interventions

Study intervention	Contact (Visit) 1	Contact 2		
Medical history	X			
Consent	X			
Baseline Questionnaires (FSDS, FSFI, custom questionnaire)	X			
Phone Interview (FSDS, FSFI, custom questionnaire)		X		

Vaginal dilators will be provided to both groups (if available) and external genital vibrators to the second (intervention) group.

- Concomitant medications – per standard treatment, patients with vulvodynia may be prescribed topical lidocaine gel and may also receive nortriptyline if there is unprovoked vulvodynia present.
- Criteria for discontinuation – if patients withdraw consent for being enrolled in the study then follow up will discontinue.
- Procedure for collecting data, including Case Report Forms (CRFs) and storage: CRFs will be filled out electronically, and stored in a password protected file. The research data will be archived for 25 years according to Queen Mary University of London/ Barts Health NHS Trust policy, JRMP SOP 20.

- Follow up will be via phone interview. Patients enrolled will receive a contact email address in case of queries in the meantime during research period.
- End of study duration will be at follow up questionnaire (at 6-24 months post initial appointment and questionnaire)

10. Assessment and management of risk

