Patients the Female Sexual Wellbeing clinic sometimes find discussions embarrassing as we discuss sexual difficulties. This is not confined to patients in the study. We aim to minimise embarrassment and difficulties discussing sensitive topics by providing a questionnaire at baseline, and a follow up phone call rather than face to face interview is also likely to help reduce embarrassment. If the pilot study suggests that patients would prefer a different form of communication then this will feed into any further research. Financial loss for participants is not expected.

The clitoral vibrators supplied to the patients in the intervention group are already available for sale to people in the UK. No published long term side effects from the use of these are known or foreseen.

Rubin et al published a clinical reference guide on sexual devices for clinicians in 2019 which stated that risks associated with sexual devices (such as vibrators) were traumatic injury or infection. Since we are recommending use of the vibrator for external use only, barrier use over sexual devices if shared, and proper disinfection to reduce risk of infection (Rubin, 2019).

In the unexpected case of an SAE this will be reported via the appropriate routes and the study management group will decide on whether the study should proceed or not. Participants will have an email address to contact the CI in case of AE or SAE.

No risks to researchers foreseen.

11. Statistical considerations

Qualitative study N/a

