11.2 Method of analysis

Qualitative analysis with thematic analysis. Some numerical analysis of formalised questionnaires, although statistical analysis will not be relevant will small numbers proposed.

12. Ethics

We do not anticipate any complex ethical, legal or management issues arising from the study at present. We are not proposing a deviation away from our current standard of care, but an additional therapy to be offered to patients enrolled in the intervention arm of the study.

Informed consent: patients will be given the opportunity to enrol in the study at the initial appointment but will be given the option to return 24hrs to one week later if they wish to enrol later.

Recruitment:

- We have necessary and exclusion criteria, one of which being requirement of use of a translator. The initial appointment and consenting for the study will involve a lot of information verbally, and translating questionnaires and patient information leaflets will not be an option for us.

Burdens foreseen:

- It is likely that explanation of the research, and how to use a clitoral vibrator, will require some additional time investment during the clinic although again we do not predict that this will have a negative impact on the quality of service offered in the clinic.
- The burden to the patient we feel will be minimal, with the offer of enrolment into the study on the day of clinic this will potentially avoid unnecessary visits. The follow up questionnaire will be via phone interview so further visits will be avoided.

Benefits foreseen:

- Patients will not receive monetary compensation but if in intervention group will receive a clitoral vibrator as part of the study which they will be able to keep

Other impacts:

Patients in our clinic sometimes find discussions embarrassing as we discuss sexual difficulties. This is not confined to patients in the study. We aim to minimise embarrassment and difficulties discussing sensitive topics by providing a questionnaire at baseline, and a follow up phone call rather than face to face interview is also likely to help reduce embarrassment. If the pilot study suggests that patients would prefer a different form of communication then this will feed into any further research.

Conflict of interest:

- None foreseen. None of the investigators are receiving any personal monetary grant or fund from study funders.

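### The primary question is whether vibration therapy is acceptable to most women, but the protocol fixes no acceptability item, cut-point or denominator and plans only a thematic analysis, which cannot show whether most accept it

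*Protocol*

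**What the plan says.** - **Primary objective (section 6.1).** The question is whether vibration therapy is "acceptable to women as part of medical management of vaginismus and vaginismus/vulvodynia, alongside current medical management".
- **Expected answer (section 5, Proposed study).** External vibration therapy "is likely to be acceptable in most women with vaginismus". This is a statement about a proportion.
- **Use of the answer (section 5.3).** The study may inform clinicians' recommendations and, "if found to be acceptable, to pave the way for studies into efficacy".
- **Primary endpoint (section 6.3).** Baseline and follow-up questionnaires are used "to assess acceptability and perceived acceptability of control therapy and intervention". No item, score or definition of an accepting woman is given.
- **Response scale (section 8, end of the text on both groups).** A line standing alone reads "4 point Likert scale 1 (Strongly disagree) to 4 (Strongly agree)". It is tied to no item and has no cut-point.
- **Analysis (section 11.2).** "Qualitative analysis with thematic analysis", followed by "Some numerical analysis of formalised questionnaires, although statistical analysis will not be relevant will small numbers proposed".
- **Statistical considerations (section 11).** "Qualitative study N/a". The synopsis also marks statistical methodology as not applicable.
- **Size of the vibrator group.** 15 in section 5 (Enrollment) and section 9; 10–15 in section 8; 15–20 per arm in section 11.1, against a total of 30.

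**The concern.** The primary objective needs an answer of the form yes, no or unclear, and the protocol's own prediction puts that answer in terms of how many women accept the therapy. Section 8 describes thematic analysis as a way of finding topics and patterns. It can explain why women accept or reject a vibrator, but it does not count them. The method named for the primary question therefore does not answer it.

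The missing definition is not deferred to another document. The protocol says that statistics do not apply. What counts as acceptable is part of the primary endpoint, so it belongs in the protocol.

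At stake is the main conclusion. With no item, cut-point, denominator or reading fixed beforehand, each can be chosen once the answers are known. In a group of about 15, those choices can decide what is reported.

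**Working it through.** **1. Which stated analysis bears on acceptability?** Section 11.2 names two. The numerical one concerns the formalised questionnaires, which sections 8 and 16.3 identify as the FSDS-R (sexual distress) and the FSFI (sexual function). Section 6.4 assigns these to the secondary endpoint. Neither measures acceptability of the treatment, so only the thematic analysis is left for the primary question.

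**2. Is there a figure to reproduce?** The protocol gives no threshold, precision or error rate. The total of 30 rests on what can be recruited: 15 + 15 = 30 agrees with section 5. Section 8's 10–15 per group gives 20–30, and section 11.1's 15–20 per arm gives 30–40, so each meets 30 only at one end.

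**3. Does the choice of reading matter?** The inputs are n = 15 in the vibrator group (section 5) and assumed true acceptability p of 40%, 50% or 83%. The 83% is quoted in sections 5 and 5.4 from women with vulvodynia who had used vibration for at least two weeks, so it is an assumption for this population. The cut-offs k are illustrations, because the protocol has none.

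- Chance of calling the therapy acceptable: P(X ≥ k) = Σ from j = k to n of C(n, j) p^j (1 − p)^(n − j).
- Exact (Clopper-Pearson) 95% limits for x of n: lower = the 2.5% point of Beta(x, n − x + 1); upper = the 97.5% point of Beta(x + 1, n − x).

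| Reading, n = 15 | Exact 95% interval at the cut-off | p = 40% | p = 50% | p = 83% |
|---|---|---|---|---|
| at least 8 | 27–79% | 0.21 | 0.50 | 0.999 |
| at least 11 | 45–92% | 0.009 | 0.059 | 0.90 |
| at least 12 | 52–96% | 0.002 | 0.018 | 0.76 |

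At a true 50%, the chance of a favourable conclusion runs from 0.50 to 0.018 depending on a choice that the protocol leaves open. Twelve is the smallest count of 15 whose lower limit exceeds 50%; for 11 of 15 it is 44.9%.

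**4. What would a strict reading cost?** Suppose the lower limit must exceed 50%, p is 83% and every woman is followed up. The chance of falling short is 1 − P(X ≥ k):

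| n | Smallest k | Chance of falling short at 83% |
|---|---|---|
| 15 | 12 | 24% |
| 14 | 12 | 43% |
| 13 | 11 | 38% |
| 12 | 10 | 33% |
| 11 | 10 | 58% |
| 10 | 9 | 53% |

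The cost depends heavily on the group size, which the protocol gives in three ways.

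**5. Does the denominator matter?** One study cited in section 5 followed up 37 of 70 women (53%). If that happened here (an assumption), about 15 × 37/70 ≈ 8 of 15 would answer. If all 8 accepted, the result would be 8 of 8 among responders (lower limit 63%) but 8 of 15 among women given a vibrator (lower limit 27%). The same data support opposite readings.

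**The case against.** The strongest reply is that this is a small qualitative feasibility study, which needs no hypothesis test. That stands, and none is asked for. A descriptive count with an interval and a stated reading is enough. Requiring a lower limit above 50% amounts to a one-sided 2.5% test and is a debatable choice at this size, so it is offered only as one option.

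Four stronger readings are tempting, and the documents do not support them.

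- **That acceptability is a formal go/no-go gate.** A reader might infer this from section 5.3. That section is background rationale, and section 13 says only that results can guide further research. No progression step or committed follow-on study is described.
- **That almost any result could be called a success.** The prediction of *most women* suggests more than half, and on that reading 0–7 of 15 would not qualify. Section 22 does expect the results to support recommending the therapy, but that is a dissemination plan, not a criterion.
- **That the 50% error rate belongs to the protocol.** It belongs to the illustrative 8-of-15 reading. The protocol states no such rule.
- **That an acceptability score is already collected and ignored.** The 4-point scale is attached to no item, and the custom questionnaire is not in the text available. It may contain a suitable item, but sections 6.3 and 11.2 do not point to one.

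**Conclusion.** The point holds in this limited form: the primary endpoint has no named item, cut-point or denominator, and the only analysis covering it cannot establish whether most women accept the therapy. The protocol marks statistics as not applicable, so the gap is not simply detail left for later.

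The practical size is shown by the illustration. With 15 women, a bare-majority reading would call a therapy acceptable to half of women acceptable 50% of the time, and the 95% interval at that count spans 27–79%. These figures rest on n = 15, full follow-up and independent responses. Figures at 83% also assume that a rate from vulvodynia patients carries over. This should be corrected because it affects the main conclusion and costs little; it does not make the study unsound.

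**What to change.** In sections 6.3 and 11.2:

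1. Name one acceptability item in the custom follow-up questionnaire at Contact 2 and state which responses count as acceptable (for example 3–4, if the item uses the 4-point scale).
2. Report the number and proportion of women given a vibrator who find it acceptable, with an exact 95% interval. Use all women given a vibrator as the denominator and count those not followed up as not shown to accept. Give the responders-only figure as a sensitivity result.
3. Before the first Group 2 follow-up, state how the count will be read, for example in bands of acceptable, uncertain and not acceptable. The sponsor chooses the threshold. A lower limit above 50% (12 of 15) is one option.
4. Reconcile the Group 2 size across sections 5, 8, 9 and 11.1, because any cut-off depends on it.
5. Report the control group's acceptability of standard therapy descriptively in the same way, since section 6.3 includes it.
6. Keep the thematic analysis to explain the reasons.

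The cost is a few sentences and no new visits; an item is added only if the questionnaire lacks one. The main downside is that a strict threshold may label a good therapy uncertain: at a true 83% with full follow-up, 24% of the time with 15 women and 33–58% with 10–14. Counting losses as non-acceptance raises this further: with about 8 of 15 followed up, 12 could not be reached. That is a reason to choose the bands with expected losses in view.

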5.4 Risks / benefits

Of 49 eligible patients with vulvodynia, 83% of those surveyed who had used vulvar vibration therapy for at least two weeks had found it an acceptable treatment (Zolnoun, 2008)

Rubin et al published a clinical reference guide on sexual devices for clinicians in 2019 which stated that risks associated with sexual devices (such as vibrators) were traumatic injury or infection. Since we are recommending use of the vibrator for external use only, barrier use over sexual devices if shared, and proper disinfection to reduce risk of infection (Rubin, 2019).

The treatment period duration is 6-12 months. other studies looking at vulvar vibration therapy as an intervention have study periods of approximately 3-6 months.. We find that this allows patients to have completed any recommended intervention.

6. Study objectives

6.1 Primary objective

Is vibration therapy (through the use of handheld vibrators on clitoral and vulval area) acceptable to women as part of medical management of vaginismus and vaginismus/vulvodynia, alongside current medical management.

6.2 Secondary objective

Does the use of clitoral/ vulval vibrators help women to progress more easily with the use of vaginal dilators compared to women not using these? Is there any self-reported difference in experiences of pleasure or enjoyment around sexual experiences in the two groups of women as reported by FSDS and FISI Scores? Do more women report enjoyable sex? Are there any differences noted in reported ability to have or enjoyment of penetrative sexual intercourse?

6.3 Primary endpoint

Baseline and follow up questionnaires will be used – to assess acceptability and perceived acceptability of control therapy and intervention.

6.4 Secondary endpoint

Baseline and follow up questionnaires will be used specific to study and also FSDS and FISI.

7. Study population

Potential participants will be identified from the patients presenting to the Female Sexual Wellbeing Clinic. Identification of participants beyond this will not be needed. The identification of suitable participants will be done by the clinicians, using the inclusion and exclusion criteria taken into account. The clinic is a joint clinic run by a clinical psychologist and medical doctor, who will be providing the initial

questionnaire and the follow up phone interview. Medical students (with honorary contract obtained) may also carry out interviews but not consent for the study.

Potential participants will be advised of the study verbally and given a written leaflet during their clinic appointment. Enrolment will be offered on the day on the understanding that the patient can decide to leave the study at any point.

Informed consent will be obtained. Consent will be taken by either the medical doctor or clinical psychologist in clinic. Verbal explanation of the study, together with a leaflet explaining the study will be provided.

If the study participants wish to enrol on the day, they will be able to. This may be preferable for convenience to avoid having to return to the clinic. Otherwise they will have 24hrs - 1 week to enrol. Enrolling on the day may be a preferred option for the patient so they do not have to return to clinic again. If they wish, they can take the written information away with them and return on another day.

Participants will enrol for approximately 6-24 months; this will be from the initial consultation until the follow up questionnaire, although no contact in the interim will be required as part of the research project there may be contact as part of any medical or psychological intervention separate to the project.

7.1 Inclusion criteria

- Able and willing to give informed consent (additional measures have to be in place if children, vulnerable adults or adults unable to give consent are included)
- Female
- Over the age of 18
- With symptoms and clinical signs consistent with vaginismus/ vaginismus and vulvodynia.

7.2 Exclusion criteria

- Unwilling or unable to give consent
- Transgender male / on testosterone therapy
- Inability to understand written and / or verbal English
- Current dermatological skin conditions requiring active treatment
- Genital herpes simplex virus symptoms within preceding 3 months
- Not reporting symptoms of vaginismus, and no evidence of vaginismus on clinical examination.

Pregnancy – via history from patient.

8. Study design

This study is a feasibility and acceptability study. The collection of qualitative data collection will be questionnaires, and interviews as described below. The data obtained will be analysed using thematic analysis to identify topics and patterns. In addition two formal, validated questionnaires will be used that can be scored to assess any change in sexual function and/or sexual distress.

Group 1 (Standard treatment)

We aim to recruit an initial 10-15 participants who will receive standard therapy with vaginal dilators and current medical management which usually consists of some or all of lidocaine gel (topical local anaesthetic applied to the vulva), tricyclic antidepressants (used in co-existing vulvodynia or vulval pain syndromes) and physiotherapy. Standard treatment also includes Group or individual psychotherapy.

Group 2 (Intervention)

In addition the standard treatment outlined above, the next 10-15 recruited will receive dilators and an external vibrator. This will take place over 6-24 months in a joint psychosexual clinic which is led by a medical doctor and a clinical psychologist.

Both groups:

Trial information will be given at the initial appointment. If the patient wishes to enrol, than an initial baseline questionnaire will be given for a patient to fill out after the clinic. A private space will be provided for the patient to do this, and there will be an offer for the patient to return to do this if preferred. Two formal, validated questionnaires will be carried out at baseline and follow up. These are the Female Sexual Distress Scale - R (FSDS) and the Female Sexual Function Index.

The follow up questionnaires will be filled out by phone contact 6-24 months after the initial consultation at the patients consent if they agree to remain enrolled in the trial for both group 1 and group 2. This will take approximately 30 mins and will be arranged at a time convenient for the patient. This interview will be carried out by a doctor. Answers will be recorded directly onto the follow up questionnaire proforma.

4 point Likert scale 1 (Strongly disagree) to 4 (Strongly agree)

9. Study procedures

- Informed consent – verbal and written will be given, patients will be offered opportunity to enrol on the day (for convenience) or to return at another point to enrol.
- Screening and recruitment – as outlined previously recruitment will be directly from clinic
- Randomization – this is a non-randomized controlled trial, as trial participants need to be identified as time goes on, and a certain number of control and intervention participants are needed. The initial 10-15 recruited will receive standard treatment, and then the next 15 will receive intervention.

Study interventions

Study intervention	Contact (Visit) 1	Contact 2		
Medical history	X			
Consent	X			
Baseline Questionnaires (FSDS, FSFI, custom questionnaire)	X			
Phone Interview (FSDS, FSFI, custom questionnaire)		X		

Vaginal dilators will be provided to both groups (if available) and external genital vibrators to the second (intervention) group.

- Concomitant medications – per standard treatment, patients with vulvodynia may be prescribed topical lidocaine gel and may also receive nortriptyline if there is unprovoked vulvodynia present.
- Criteria for discontinuation – if patients withdraw consent for being enrolled in the study then follow up will discontinue.
- Procedure for collecting data, including Case Report Forms (CRFs) and storage: CRFs will be filled out electronically, and stored in a password protected file. The research data will be archived for 25 years according to Queen Mary University of London/ Barts Health NHS Trust policy, JRMP SOP 20.

- Follow up will be via phone interview. Patients enrolled will receive a contact email address in case of queries in the meantime during research period.
- End of study duration will be at follow up questionnaire (at 6-24 months post initial appointment and questionnaire)

10. Assessment and management of risk

Patients the Female Sexual Wellbeing clinic sometimes find discussions embarrassing as we discuss sexual difficulties. This is not confined to patients in the study. We aim to minimise embarrassment and difficulties discussing sensitive topics by providing a questionnaire at baseline, and a follow up phone call rather than face to face interview is also likely to help reduce embarrassment. If the pilot study suggests that patients would prefer a different form of communication then this will feed into any further research. Financial loss for participants is not expected.

The clitoral vibrators supplied to the patients in the intervention group are already available for sale to people in the UK. No published long term side effects from the use of these are known or foreseen.

Rubin et al published a clinical reference guide on sexual devices for clinicians in 2019 which stated that risks associated with sexual devices (such as vibrators) were traumatic injury or infection. Since we are recommending use of the vibrator for external use only, barrier use over sexual devices if shared, and proper disinfection to reduce risk of infection (Rubin, 2019).

In the unexpected case of an SAE this will be reported via the appropriate routes and the study management group will decide on whether the study should proceed or not. Participants will have an email address to contact the CI in case of AE or SAE.

No risks to researchers foreseen.

11. Statistical considerations

Qualitative study N/a

